On arrival to the laboratory, subjects will be asked to empty their bladder to minimize the influence of reflex sympathetic activation on peripheral vascular tone. In the supine position, subjects will be instrumented with a single-lead ECG (lead II; Powerlab model ML132, ADInstruments). Beat-to-beat systolic (SBP), diastolic (DBP), and mean (MAP) blood pressures will be recorded continuously from the right hand (Finometer; Finapres Medical Systems BV, Arnhem, Netherlands), while discrete blood pressures will be taken every minute from the left arm (Carescape V100; GE Healthcare, Milwaukee, WI, USA). Following instrumentation, baseline recordings will be made during a 10 minute supine rest period. Data acquisition will be performed as detailed above. Subjects will then be passively moved to an upright seated or stand position by the investigators using the cardiac chair or the tilt table. This position will be maintained for 15 minutes, during which recordings of heart rate and blood pressure will be continued.

Cardiac Structure and Function Duration. 20 minutes.

Cardiac assessments will be performed using ultrasound while the subject is in the supine, sitting and standing position. Heart rate will be recorded during the assessment using a single-lead ECG. An ultrasound probe covered in gel will be placed on the subject's chest (Vivid 7; GE Healthcare, Horten, Norway). Cardiac images for 5 cardiac cycles will be collected in the parasternal long and short axes, and apical views. Images will be analyzed offline to determine indices of structure, systolic and diastolic function, and strain. A detailed description of the outcome measures is described in Table 1. These metrics will be recorded at supine baseline, in the seated position and standing with assistance during the aforementioned orthostatic sit-up test.

Cardiac Structure and Function in SCI subjects with Epidural Stimulation Implant

Individuals with epidural stimulation implant would have the above mentioned cardiac structure and function assessment in the following positions:

- 1) Supine no stimulation

2) Supine Stimulation

3) Sit-up no stimulation

4) Sit-up Stimulation

The stimulation parameters used would be at low voltages not to induce leg muscle contraction and at a frequency that would maintain and/or regulate the blood pressure to within normal ranges.

Neurocognitive Assessment. 15 minutes.

This test can be conducted at the same time as cardiac structure and function.

A visual task will be employed to activate the occipital lobe (while measuring posterior cerebral artery blood flow velocity (PCAv)), and a verbal fluency task to preferentially activate the left cerebral cortex (while measuring middle cerebral artery blood flow velocity (MCAv)), the order of which was randomized. Three minutes of baseline data, as well as a mock practice will be recorded to ensure hemodynamic homeostasis. After this, 10 cycles will occur, each consisting of 30 seconds eyes closed followed by 30 seconds reading. An auditory stimulus will provide notification of 'reading' and 'eyes-closed' periods. The velocity response will be averaged for all 10 trials for each participant. The verbal fluency task has the combined benefit of having been shown to preferentially activate the left MCA, and be a valid and ubiquitous marker of cognition. A PowerPoint (Microsoft, Redmond, WA, USA) slide show will be used, consisting of a series of 10 slides presenting a single letter for 30 seconds followed by the words 'Eyes Closed' for 30 seconds. The ten letters will be M, H, O, I, W, B, T, F, A, S. The letters will be separated into two stages (i.e., self-reported word totals versus verified word totals) separated by two minutes, the order of which will be randomized.

Cerebrovascular Assessment. 20 minutes.

This test can be conducted at the same time as cardiac structure and function.

For each participant, brachial BP will be measured (BpTRU-BPM-100, Coquitlam; VSM Medical, Vancouver, BC, Canada) on the right brachial artery. The following will be sampled at 1,000 Hz using an analog-to-digital converter (Powerlab/16SP ML 795; ADInstruments, CO Springs, CO, USA) interfaced with data acquisition software on a laptop computer (LabChart 7 ADInstruments): non-invasive beat-by-beat BP measurement via finger photoplethysmography (Finometer PRO, Finapres Medicine Systems, Amsterdam, The Netherlands), electrocardiogram (ML 132; ADInstruments), PETCO₂ (CO₂ Analyzer Gold Edition-17515, Ventura, CA, USA), velocity in the left middle cerebral artery (MCAv) or right posterior cerebral artery (PCAv; Doppler-Box, Compumedics DWL, Singen, Germany). These arteries will be insonated using a 2 MHz probe mounted on the temporal bone and a fitted head strap. As described in depth elsewhere, the P1 segment of the PCA will be insonated at depths between 60 to 70 mm, whereas the MCA was insonated from 45 to 55 mm. Arteries will be confirmed using ipsilateral common carotid artery compression, ensuring an increase in PCA velocity and decrease in MCA velocity. These metrics will be recorded throughout the aforementioned orthostatic sit-up test and following neurocognitive assessment.

Arterial Stiffness. 15 minutes.

aPWV (m/s) is calculated by dividing the distance between measurement sites, by the pulse transit time. Distance between the carotid and femoral arteries will be measured using measuring tape along the surface of the body, held parallel to the testing table. The pulse transit is determined from the arterial blood pressure waves, which are collected at each arterial site. A pen-like device (model SPT-301; Millar Instruments Inc., Houston, TX) will be applied to the carotid and femoral arterial sites using a light pressure to obtain arterial pressure waves. Heart rate will be recorded using a single-lead (lead I) electrocardiogram (ECG) (model ML 123, ADInstruments Inc., Colorado Springs, CO).

Arterial structure: Wall thickness and lumen diameter. 30 minutes.

Brachial and femoral arterial images will be collected using B-mode ultrasound (INFO) for 10 cardiac cycles. Images will be analyzed using internal ultrasound software to determine lumen diameter and intima-media thickness.

Test	Dependent variable	Evaluation of data	Comments
1. Resting hemodynamics and Orthostatic sit-up test	Resting supine arterial blood pressure (BP) and heart rate (HR), BP and HR response to a 10 min sit-up test	The presence of orthostatic hypotension (OH) will be considered when there is a decrease in either systolic BP of 20 mmHg or diastolic BP of 10 mmHg when upright (seated) – based on the definition for OH by the Consensus Committee of the American Autonomic Society and the American Academy Neurology.	The presence of orthostatic hypotension would suggest severely disrupted autonomic control in the evaluated individual.
2. Cardiac structure and function	
STRUCTURE
 
LV systolic/ diastolic diameters, LV systolic/ diastolic volumes, LV mass, Septal and posterior wall thickness
 
SYSTOLIC FUNCTION
 
Ejection fraction, Stroke volume, Cardiac output, Systolic myocardial tissue velocity from the septal wall (S')
 
DIASTOLIC FUNCTION
 
Early (E) and late (A) transmitral filling velocity; E/A ratio, Deceleration time (Dt), Isovolumetric relaxation time (IVRT), Early (E') and late (A') myocardial filling velocity from the septal wall, E/E'
 
2D Strain
	Indices of cardiac structure and function will be determined from offline analysis of ultrasound images using standard analysis packages available on the ultrasound.	Cardiac dysfunctions, identified using echocardiographic (ultrasound) assessments are associated with an increased risk of CVD.
3. Neurocognitive Assessment	EXECUTIVE FUNCTION	Concurrent cerebral blood velocity evaluation	
4. Cerebrovascular Assessment	CEREBRAL AUTOREGULATION		

Test	Dependent variable	Evaluation of data	Comments
	Transcranial Doppler evaluation of middle and posterior cerebral artery blood flow concurrent with changes in beat-by NEUROVASCULAR COUPLING Transcranial Doppler evaluation during cognitive assessments		
5. SSRs	Number of present sympathetic skin responses, Latency		

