The Epworth Sleepiness Scale will be administered during a subject interview.

Falls Diary

The falls diary will be a subject-maintained log of fall events. The information will include the time and date of the fall, the activity prior to the fall, the estimated height of the fall, the presence of head or bodily injury after the fall, and subject recorded medical information such as the need for hospitalization and diagnoses related to the falls.

Urinary Function

Urinary function will be assessed through the Neurogenic Bladder Symptom Score (NBSS) survey.

Bowel Function

Bowel function will be assessed through the Neurogenic Bowel Dysfunction Score survey.

MODIFIED PROCEDURES

Modified procedures are listed in detail below. All procedures are explained in working detail in the MOP.

Treatment/Intervention Data

Home Training

Home training allows use of the epidural stimulator while completing a computer-guided accelerometer-based task. Subjects will fasten two wireless accelerometers to their feet to detect plantarflexion and dorsiflexion as well as gross translational movement in the legs.

Our group has developed an android app that cues the subject to move the left or right foot in a randomized fashion. As the subject moves their legs, the accelerometry data will be collected wirelessly and stored. This data will include the subject number, date and time logs, stimulator setting number, and accelerometry data. The stored data will be automatically uploaded to a HIPAA-compliant and secure server. Post-processing will allow calculation of maximum velocity and fidelity of volition.

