After the first visit, subjects will be given detailed instructions on their home stimulation program, which allows up to four hours per day of epidural stimulation. At each follow-up visit, the subjects' SCS programmers will be customized with 5 subject settings. Only experimental stimulator configurations (no sham settings) will be used. Subjects will receive a paper calendar with assigned subject settings for one hour of training 5 times per week. Subjects are expected to turn the stimulator on for training, but can otherwise use the stimulator up to 4 hours per day as needed. Subjects will be instructed to undergo a formal regimen of exercises and will be supplied with a tablet computer capable of cuing subjects with audio and video through the exercises and tracking wireless accelerometer data during the session. Fidelity of the volition cuing will be calculated as a percentage of the training session when the entire training session is completed. Maximum velocities will be aggregated over the training session and parameterized for comparison with repeated measures ANOVA. Stimulator use time will be logged and factored into data analysis.

Electrodiagnostics

Brain Motor Control Assessment. 60 minutes.

The subject's quadriceps, adductors, hamstrings, tibialis anterior, and triceps surae muscles of each leg, as well as the midline over the abdominal muscles at the level of the umbilicus and the lumbar paraspinal muscles will be recorded with multichannel surface EMG. Upper leg and ankle accelerometers will also be monitored to test for presence of movement. Subjects will undergo relaxation, voluntary and passive hip and knee flexion, and voluntary and passive ankle dorsiflexion and plantarflexion during trials of computer controlled patterns and levels of epidural stimulation (or sham). Stimulation and sham programs, defined as stimulator settings that either involve an experimental stimulation configuration or no stimulation through any lead, will be randomly assigned in a group of repeated trials during the session. The BMCA Lower-Limb Protocol elements of Relaxation, Voluntary movements, and Passive stretch will be used to gather quantitative EMG data. Accelerometer data will be quantified by presence and rate of acceleration.

Device electrode custom mapping assessment

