10.4.3 ANALYSIS OF THE SECONDARY ENDPOINT(S)

Clinical Decision Support System (CDSS)

Optimal programming of the spinal cord stimulator system is seen as a major future barrier to future widespread use, and, as a result, a major goal and specific secondary outcome of the study is exploration of the parameter space of epidural spinal cord stimulation. Current implantable pulse generators offer frequency, pulse width, amplitude, and electrode configuration as programmable parameters of continuous stimulation. While our expectation of future systems is increased freedom in the parameter space with more numerous parameters, more than 32 million settings can currently be programmed, far exceeding the number of parameters that could be evaluated in any clinical trial.

To overcome this daunting barrier to future clinical use, this study intends to populate a probabilistic model of the parameter space that is able to grow with the addition of each patient. Subthreshold testing of the stimulator system during clinical visits reduces the dimensionality of the parameter space by eliminating amplitude as significant, leaving frequency and pulse width.

At each visit, subjects will be assigned 8 randomly chosen clusters from the parameter space as a basis for response surface modeling. Subjects will be programmed 8 randomly sorted settings corresponding to one sample from each of the 8 clusters at each clinical appointment. During the month between clinical appointments, subjects will link their home volitional movement testing to the scheduled setting, which will assess velocity of their movements and fidelity of movement through randomized cuing. In turn, each setting will be assigned outcomes from their home testing. Each of the 8 settings will correspond to one of the 8 clusters being evaluated in the parameter space and each monthly visit will evaluate nearest neighbor settings until the response surface gradient can be calculated. Once the corresponding response surface gradient can be calculated, subjects will be programmed to descend the gradient until the end of the trial.

More specifically, the St. Jude Medical Proclaim Elite neurostimulators currently offer the following parameters:

Frequency: 2-100 Hz by 2s = 50 settings, 110 - 1200 by 10 = 110 settings

Pulse Width: 10-1000 us by 10: 100 settings

Amplitude: 0-25.5 by 0.1: 256 settings

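### The CDSS response surface compares settings used in different months with no month term, so a home-training gain would be mixed with the effect of setting

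*Combined protocol and SAP*

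**What the plan says.** Under Clinical Decision Support System, section 10.4.3 takes one setting from each of 8 clusters at each visit, in random order, for home use during the following month. It then says: "In turn, each setting will be assigned outcomes from their home testing". Local exploration runs over visits: "each monthly visit will evaluate nearest neighbor settings until the response surface gradient can be calculated". After that, "subjects will be programmed to descend the gradient until the end of the trial". Amplitude is dropped from the search ("eliminating amplitude as significant, leaving frequency and pulse width"), so the surface has two dimensions.

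Section 7.1.1, Home Training, describes the data behind this. The programmer holds 5 settings, a conflict with the 8 of section 10.4.3 that the text does not resolve. There is no home control: "Only experimental stimulator configurations (no sham settings) will be used". The stated analysis is brief: "Maximum velocities will be aggregated over the training session and parameterized for comparison with repeated measures ANOVA", with no factors named. The same paragraph adds: "Stimulator use time will be logged and factored into data analysis". The app keeps what an adjustment would need: "This data will include the subject number, date and time logs, stimulator setting number, and accelerometry data".

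Section 10 contains no model for the home data with a month, period or use-time term, and no plan to repeat an earlier setting.

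**The concern.** Neighbouring settings within a cluster are tested in different months, and the later one is tested after more training. A difference between them is the setting effect plus whatever the subject gained in between. Without a home sham, a repeated setting or a month term, the stated rule cannot separate the two.

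The CDSS is a named secondary objective. Section 10.4.1 says the longitudinal assessments look for improvement over time as knowledge of the parameter space grows, and section 10.4.2 mentions time course and plasticity as of interest. If training helps, a descent over a completely flat surface would still look like a success, and the surface handed to later patients would carry the same error.

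**Working it through.** **The plan's own figures.** No sample size or power is given for the CDSS. Its counts reproduce: (50 + 110) × 100 × 256 = 4,096,000; × 8 = 32,768,000; 160 × 100 = 16,000. The primary sample size also reproduces: f = (0.2/2)/0.25 = 0.4, m = 9, ρ = 0.5, alpha 0.025, λ = 0.4² × 56 × 9 / (1 + 8 × 0.5) = 16.1, power 0.954 at N = 56. That contrast is made within visits and does not use the home data.

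**Timing.** Read as fixed clusters explored locally, two parameters need a base setting and one neighbour in each direction, hence three monthly visits. Neighbours are then tested one and two months after the base. At 4.348 weeks a month, 5 h/week (7.1.1) is 21.7 h per month and 20 h/week (the maximum in 6.1.11) is 87.0 h. Two months is 43.5 to 173.9 h.

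**Local comparison on a flat surface.** Assumptions: session SD 1, independent sessions, 21.74 one-hour sessions a month shared by K settings, and a gain of g SD per month. The SD of a difference between two settings is √(2K/21.74), which is 0.858 for K = 8 and 0.678 for K = 5. P(later looks better) = Φ(g/SD) one month apart and Φ(2g/SD) two months apart.

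| g per month | K=8, 1 month | K=8, 2 months | K=5, 1 month | K=5, 2 months |
|---|---|---|---|---|
| 0 | 50% | 50% | 50% | 50% |
| 0.05 | 52% | 55% | 53% | 56% |
| 0.1 | 55% | 59% | 56% | 62% |
| 0.2 | 59% | 68% | 62% | 72% |
| 0.3 | 64% | 76% | 67% | 81% |

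Subtracting the mean change of the other settings in use that month returns every cell to 50%.

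**Descent phase.** Months 3 to 15 give 12 home months, and three to form a gradient leave nine. At a constant gain, nine months on a flat surface show 9g = 0.45, 0.9, 1.8 or 2.7 SD of improvement for g = 0.05, 0.1, 0.2 or 0.3. All of it is training.

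**Pooled surface.** Simulation with 56 subjects, 12 months, 8 settings and a true slope of 0; 5 to 20 h/week; gain proportional to hours; subject SD 0.5; subject-month SD 0.3.

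- All steps one way in frequency, at an assumed 5 grid steps a month: the false slope across the range is 0.28, 0.55, 1.11 and 1.66 SD for g = 0.05 to 0.3 without a month term. It is at most 0.005 SD with subject, month and hours in the model.
- Random directions: the mean slope bias is 0. At the largest gain the spread of the slope grows from 0.026 to 0.069 without a month term, and stays at 0.026 to 0.030 with one.
- Random directions, shape of the surface: a flat surface acquires false curvature of 0.12 to 0.72 as g goes from 0.05 to 0.3, in proportion to the gain (0.72/0.12 = 0.3/0.05 = 6). This can happen when paths move outward, because later months then lie nearer the edges of the range. The size depends on the layout of steps, so only the direction and proportionality should be relied on. The month term removes it without loss of precision.

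**Can a month term be estimated?** Not within one isolated cluster: three observations and four parameters, rank 3. It can be when the settings used in the same month share it: 8 clusters with varied directions and a common gradient give rank 11 of 11.

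**Steering of individual subjects.** With a true slope of 0.2 SD per step and random directions, the share of wrong-way steps is:

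| | g = 0 | g = 0.3 |
|---|---|---|
| K=8, unadjusted | 0.407 | 0.417 |
| K=8, month-adjusted | 0.408 | 0.413 |
| K=5, unadjusted | 0.374 | 0.396 |
| K=5, month-adjusted | 0.396 | 0.390 |

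Single steps are mostly noise with or without adjustment.

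**The case against.** Several parts of the other side's case are sound.

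- **Use time is promised.** A reader might infer that the plan ignores training exposure altogether. Section 7.1.1 says otherwise. What is missing is the form of the adjustment and its place in the CDSS model, and an hours term does not by itself remove a month effect.
- **Clusters may be redrawn.** Section 10.4.3 can be read as drawing 8 new clusters at each visit. The local table above would then not apply, and mainly the descent phase is exposed. Eight concurrent settings could also support a fit within the month, which is protected. So the text does not support the broader inference that every training gain goes to the later-tested setting.
- **The large slopes are assumed.** The 0.28 to 1.66 SD figures need every subject to step the same way, and nothing in the documents says so. The 0.45 to 2.7 SD figures need a gain that does not level off.
- **Steering hardly changes.** A reader might infer that subjects would be programmed in the wrong direction. The steering check does not show that; with 5 settings and no gain, adjustment makes it slightly worse.
- **Hours can follow from the setting.** Use beyond the training hour is as needed, so cumulative hours may reflect how well a setting works. That argues against hours as a main-model term.
- **The analysis is preliminary.** Section 10.2 gives the CDSS no hypothesis, section 10.4.9 calls secondary outcomes preliminary, and stored dates allow a later correction.

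What survives is that the rule as written compares across months without a month term. It is better to fix that in advance than to choose a correction after seeing the surface.

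**Conclusion.** The concern holds for the final CDSS surface and for any claim that descent improved performance. Section 10.4.3 makes month part of the comparison and gives no term to remove it, and the promise about use time does not fill the gap. The size is conditional. With no training gain there is no bias. At 0.05 to 0.3 session SD per month, the later neighbour is favoured in 52% to 81% of flat-surface comparisons, depending on the gain, the interval and whether 5 or 8 settings are in use. Gains, SDs and step sizes are all assumptions, since the documents state none. Contrasts among settings used in the same month are protected.

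A reader might go further and doubt the primary result. The documents do not support that: stimulation and sham are randomised within each visit, and neither the contrast nor the 56 subjects depends on home data. This should be corrected, but it concerns a secondary, model-building objective.

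**What to change.** Add to section 10.4.3: *The final CDSS and home velocity and fidelity data will be fitted with a mixed model containing a subject effect, month as a category within subject (shared by all settings in use that month), and frequency and pulse-width terms that allow curvature. Setting effects will therefore come from within-month contrasts. The direction of each neighbouring setting will be drawn at random.* Taking month within subject removes any gain common to a subject's settings that month, whether or not it tracks hours.

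In section 7.1.1, replace the general promise about use time with a statement that cumulative hours will be reported as a sensitivity covariate in this model.

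State that improvement during descent will not be attributed to better settings unless a reference setting is repeated. Repeating one takes 1 of the 5 or 8 slots in the months it is run.

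Month-adjusted steering of individual subjects can stay optional. It raises the noise of a single-cluster difference by about 7% with 8 settings (0.919 against 0.860) or 12% with 5 (0.759 against 0.679), and changes wrong-way steps little.

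The cost is a little analysis work and a few sentences, with no added visits or subjects; date, time, setting number and use time are already recorded. The downside is that a gain common to all of a month's settings cannot be credited to descent.
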